5.7.3 Kaplan-Meier for EHS

The time to EHS is defined as the length of time from the treatment initiation to the development of extrahepatic spread of the disease via imaging assessment.

The data items to be considered will include:

- The date of the extrahepatic spread in the Overall Response form
- The very last date by scanning all available dates in the database
- The desired cut-off days

5.7.4 Kaplan-Meier for PPF

PPF is defined as the length of time from the treatment initiation, that treated subjects are still progression-free.

The data items to be captured will include:

- The date of the disease progression in the Overall Response form
- The very last date by scanning all available dates in the database
- The desired cut-off days

The proportion of any time point will be determined by the Kaplan-Meier estimates.

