12.1.2. Secondary Endpoints

The study is not powered for the secondary endpoints therefore there are no formal hypotheses. The secondary endpoints and analyses are shown below.

Kaplan-Meier analyses will be used for time-to-event type of endpoints such as overall survival (OS), time to progression (TTP), and time to extrahepatic spread through 12 months. A binary proportion will be presented for ORR at 30-day and 3-month and progression-free (PPF) rate at 12 months. A frequency will be provided for treatment associated adverse events.

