5.7 Time-To-Event Kaplan-Meier Analysis

The Kaplan-Meier product-limit method will be used to estimate event or event-free rates for time-to-event outcomes as post-hoc analyses, such as OS, TTP, EHS, and PPF through 12 months.

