5.7.1 Kaplan-Meier for OS

OS is defined as the length of time from the treatment initiation, that treated subjects are still alive. The Kaplan-Meier analysis is aimed to capture the all-cause death for each subject. Subjects who are lost-to-follow will be considered being censored.

There are three critical data items to be captured:

- Death date
- The very last date in the database (e.g. follow-up visit date and/or site reported AE date)
- The desired cut-off days (e.g. 6-month OS at 182 days, 12-month OS at 365 days)

In addition to the Kaplan-Meier survival curve, the median survival time (mOS) will also be used to represent the study cohort.

5.7.2 Kaplan-Meier for TTP

TTP is defined as the length of time from the treatment initiation to either the date of the first disease progression occurred, as assessed by the investigators, or the date of the subject died due to any cause, whichever comes earlier.

TTP (also referred as "time to treatment failure") will be measured by a few data items list below:

- The date of the disease progression in the Overall Response form
- The date of lost-to-follow due to:
 - o Adverse events
 - o Progressive disease/insufficient therapeutic response
 - Death
 - o Failure to return
 - o Refusing treatment/being unwilling to cooperate/withdrawing consent
- The very last date by scanning all available dates in the database
- The desired cut-off days

In addition to the Kaplan-Meier estimates, the median will also be used to represent the study cohort.

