7.1 Derivation of Variables

- The number of subjects included in the event rates (overall and individual components) will be based on subjects who have adequate follow-up and/or have experienced any component of events within the analysis interval.
- The last follow-up date will be the latest of the following dates for each subject: onset date of an event, DEB-TACE dates, treatment evaluation follow-up dates, end of study date, end of treatment date, and follow-up visit dates.
- Days to event (or last known status) = event (or status) date index procedure date (e.g. DEB TACE1).

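### SAP 5.7.3 gives no rule for death in the Kaplan-Meier analysis of extrahepatic spread; its data items imply censoring, which can modestly overstate the 12-month spread rate

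*SAP*

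**What the plan says.** Protocol 12.1.2 names time to extrahepatic spread (EHS) among the secondary endpoints to which the product-limit method applies: "Kaplan-Meier analyses will be used for time-to-event type of endpoints". SAP 5.1 repeats this. SAP 5.7 adds that the output is a rate: "The Kaplan-Meier product-limit method will be used to estimate event or event-free rates for time-to-event outcomes", with EHS on the list and 12 months as the horizon.

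SAP 5.7.3 gives the definition: "The time to EHS is defined as the length of time from the treatment initiation to the development of extrahepatic spread of the disease", established by imaging. It then lists three data items:

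- the event date: "The date of the extrahepatic spread in the Overall Response form";
- the end date otherwise: "The very last date by scanning all available dates in the database";
- the cut-off day.

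Death appears neither in the definition nor in the list. SAP 7.1 defines the end date further: "The last follow-up date will be the latest of the following dates for each subject". The dates it names include the end-of-study date, and Protocol 11.10 and the synopsis treat death as a form of study exit.

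Two neighbouring sections do address death. SAP 5.7.1 collects the death date for overall survival. SAP 5.7.2 makes death an event for time to progression (TTP): "or the date of the subject died due to any cause, whichever comes earlier". The one explicit censoring sentence in SAP 5.7 concerns loss to follow-up in the survival analysis. Neither document names a competing-risk method.

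**The concern.** A subject who dies without spread can never develop it. For this endpoint death is therefore a competing event, unlike loss to follow-up, after which spread may still occur unseen.

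If deaths are censored, Kaplan-Meier takes the dead subject out of the risk set and lets the survivors' later spread hazard stand in for that subject, as though spread were still possible. One minus Kaplan-Meier then estimates spread in a hypothetical setting without death (a net risk). It does not estimate the share of treated subjects who develop spread within 12 months. A reader shown a 12-month spread rate will normally take it as the second quantity.

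At stake is the interpretation of one descriptive secondary result. There is also a programming ambiguity, because whoever writes the code must supply the rule for death.

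**Working it through.** **1. What the text implies about death.** Take a subject who dies without recorded spread. The first data item in SAP 5.7.3 is empty, so there is no event. Follow-up ends at the last available date, which under SAP 7.1 can be the end-of-study date. In a Kaplan-Meier analysis, no event plus an end date before the cut-off is a censored observation. This is an inference from the listed items; no sentence states it.

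**2. Figure to reproduce.** The documents state no expected EHS rate, precision or sample size for this endpoint, so there is no plan figure to check. The trial's size rests on the 6-month response rate only.

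**3. Inputs.**

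- 12-month spread, F, as one minus Kaplan-Meier: assumed, 5% to 30%.
- 12-month mortality without spread, D: 0% to 19%. The only figures in the documents are one-year survival of 100% (Child-Pugh A) and 81% (class B) in SAP 5.10.2. They describe chronic liver disease in general, and class B there covers 7-9 points, while only B7 is eligible.
- Independent, constant hazards over one year.

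**4. Formulas.**

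- Spread hazard h = -ln(1 - F); death hazard m = -ln(1 - D).
- One minus Kaplan-Meier with deaths censored: 1 - exp(-h) = F.
- Cumulative incidence: CIF = h/(h + m) × [1 - exp(-(h + m))].

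**5. Worked case, F = 10%, D = 19%.** h = 0.1054 and m = 0.2107. Then h/(h + m) = 0.3333 and exp(-(h + m)) = 0.90 × 0.81 = 0.729. CIF = 0.3333 × 0.271 = 9.0%. The overstatement is 1.0 point.

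**6. Range.**

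| One minus Kaplan-Meier | Mortality | CIF | Overstatement (points) |
|---|---|---|---|
| 5% | 19% | 4.5% | 0.5 |
| 10% | 0% | 10.0% | 0 |
| 10% | 5% | 9.75% | 0.25 |
| 10% | 10% | 9.5% | 0.5 |
| 10% | 19% | 9.0% | 1.0 |
| 20% | 10% | 19.0% | 1.0 |
| 20% | 19% | 18.1% | 1.9 |
| 30% | 19% | 27.2% | 2.8 |

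Over this range the overstatement is 0 to 2.8 points, or 0% to about 11% of the CIF.

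**7. Against sampling error.** Simulated trials of 109 subjects with F = 10% and D = 19% gave a mean one minus Kaplan-Meier of 10.1% and a mean Aalen-Johansen estimate of 9.1%. The standard deviation of one minus Kaplan-Meier was about 3.1 points. With F = 20% and D = 19% the means were 19.9% and 18.0%, and the standard deviation was about 4.0 points.

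**8. Spread found only at visits.** Suppose spread is seen only at days 30, 91, 183 and 365, and a death before a visit prevents detection there. For each interval of length d days, q = 1 - (1 - F)^(d/365) and s = (1 - D)^(d/365), and the CIF is the sum of (proportion alive and free of detected spread at the start) × s × q. For F = 10%, D = 19% the four terms are 0.0085 + 0.0164 + 0.0230 + 0.0393 = 8.7%. F = 20% gives 17.5%. F = 30% gives 0.0284 + 0.0533 + 0.0708 + 0.1104 = 26.3%. The gaps are 1.3, 2.5 and 3.7 points. The 2.8-point ceiling thus belongs to the constant-hazard model with spread dated when it occurs.

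**The case against.** **Censoring of deaths is not written down.** This stands. The list in SAP 5.7.3 does not claim to be complete, and the sponsor may intend another rule. What the text supports is that the handling of death is unspecified and that the listed items lead to censoring.

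**The size is assumed.** This stands too. Neither document gives a spread or mortality rate for the trial. Eligible subjects have Child-Pugh A or B7, ECOG 0 or 1 and no extrahepatic spread at entry, so early deaths may be few and the overstatement close to zero. In the simulated cases it is well below one standard deviation of the estimate. It is nevertheless systematic and in one direction, and sampling error does not offset it.

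**Nothing is decided on this endpoint.** Correct. SAP 5.1 sets no hypotheses for secondary endpoints and calls the additional assessments observational. SAP 5.7 even labels the Kaplan-Meier analyses post hoc.

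**A net Kaplan-Meier estimate is legitimate.** It is, if independent censoring is plausible and the estimate is labelled as net. The SAP provides no such label and speaks of event rates.

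Two stronger readings are tempting. A reader might infer that SAP 5.7.2 and 5.7.3 contradict each other because TTP counts "the date of the subject died due to any cause, whichever comes earlier" and EHS does not. They define different events, a composite and spread alone, so the contrast is not a contradiction. A reader might also infer that Kaplan-Meier keeps dead subjects at risk. It removes them. Actually keeping them in the risk set to day 365 would, apart from other censoring, return the cumulative incidence.

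**Conclusion.** The point holds as a minor one. SAP 5.7.3 leaves death without spread unaddressed, its data items imply censoring, and no competing-risk estimator is planned. On that reading one minus Kaplan-Meier equals the actual 12-month proportion with spread if no death without spread precedes a later spread event, and exceeds it otherwise. The direction does not depend on the assumed rates.

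The size does. Across the assumed ranges it runs from zero to about 2.8 percentage points under constant hazards, and somewhat more if spread is detected only at visits. These inputs are illustrations, not trial assumptions. The primary endpoint, type I error and study success are not touched.

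**What to change.** In SAP 5.7.3, state that the 12-month EHS rate is estimated by the cumulative incidence function (Aalen-Johansen), with death without prior spread as a competing event. Add the death date to the data items. If a Kaplan-Meier curve is kept, present it as supportive and label it a cause-specific (net) estimate with deaths censored.

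The data items for proportion progression-free in SAP 5.7.4 also omit death, so a sentence on its handling there would be useful at the same time.

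The cost is one or two SAP sentences and a standard estimator. No new data are needed, because death dates are already captured for overall survival. The downside is small: a second curve to explain if both are shown.

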5.8 Time to Events and Time to Adequate Follow-Up

The safety binary rates (specified in the Safety Plan), as opposed to Kaplan-Meier rates, will be calculated based on the subjects who have adequate follow-up and/or have experienced prespecified events.

All reported AEs will be summarized as the safety outcome. The three protocol-defined safety events listed below are only monitored for safety trigger:

- All-cause death
- Liver failure
- Hepatic abscess

5.8.1 Event Rates Presented Using "Month" System

The denominator will be based on number of subjects who reach the protocol-defined lower window (i.e. adequate follow-up days) and/or subjects who experience the event. The numerator will be based on number of subjects-level events within the protocol-defined upper window. Subject-level events beyond the upper window will be counted as next visit.

Follow-up Visit	Protocol Defined Lower Window	Protocol Defined Upper Window
1 Month	16	44
3 Months	77	105
6 Months	169	197
12 Months	351	379

5.8.2 Event Rates Presented Using Exact Days Cut-Off System

The denominator will be based on number of subjects who reach the protocol-defined lower window (i.e. adequate follow-up days) and/or subjects who experience the event. The numerator will be based on number of subjects-level events within the exact desired cut-off days. Subject-level events beyond the exact cut-off days will be counted as next cut-off days.

Follow-Up Cut-Off	Days for Adequate Follow-Up	Maximum Days to Event
30 Days	16	30
91 Days	77	91

Follow-Up Cut-Off	Days for Adequate Follow-Up	Maximum Days to Event
183 Days	169	183
365 Days	351	365

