5.9 Analysis of Site-Reported Serious and Non-Serious Adverse Events

Subject-level event rates will be calculated at various time points (e.g. exact days) based on all events reported by the site regardless of whether or not they are ultimately adjudicated. These safety parameters will be summarized using descriptive statistics.

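### The SAP's adequate-follow-up denominator keeps subjects with an early event but drops event-free early withdrawals, so cumulative 6- and 12-month safety rates rise with attrition alone

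*SAP*

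**What the plan says.** The opening of SAP 5.8 concerns the binary safety rates that a separate Safety Plan defines. It says of them: "as opposed to Kaplan-Meier rates, will be calculated based on the subjects who have adequate follow-up and/or have experienced prespecified events". It lists all-cause death, liver failure and hepatic abscess as events monitored for safety triggers only.

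SAP 5.8.1 (visit windows) and 5.8.2 (exact days) both define the denominator as the "number of subjects who reach the protocol-defined lower window (i.e. adequate follow-up days) and/or subjects who experience the event". The lower windows are days 16, 77, 169 and 351. On the numerator, 5.8.2 says: "The numerator will be based on number of subjects-level events within the exact desired cut-off days". SAP 5.8.1 adds: "Subject-level events beyond the upper window will be counted as next visit". SAP 5.8.3 counts all event rates from the procedure date.

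SAP 7.1 gives the programming rule with a different condition: "subjects who have adequate follow-up and/or have experienced any component of events within the analysis interval".

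SAP 5.9 plans subject-level rates of site-reported events at several time points, with exact days as the example, and names no denominator. SAP 5.7 plans Kaplan-Meier estimates only for overall survival, time to progression, extrahepatic spread and progression-free proportion. For the named secondary endpoint, Protocol 12.1.2 says only: "A frequency will be provided for treatment associated adverse events". SAP 5.1 repeats this.

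**The concern.** Whether a subject stays in the denominator depends on the outcome. Someone with an event on day 5 who leaves on day 40 is counted in the numerator and denominator of the 12-month row. Someone event-free who withdraws in month 8 is in neither. The 6- and 12-month rates therefore mix toxicity with attrition, and a rise from row to row can look like late toxicity when nothing new has happened.

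Safety is part of the primary objective, and adverse-event frequency is a named secondary endpoint. In a single-arm study these rates have no concurrent control that would share the distortion. Apart from overall survival, which covers all-cause death, no planned analysis gives a censoring-adjusted rate for a safety event.

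The wordings also disagree. Sections 5.8.1 and 5.8.2 keep a subject who had the event in question. The opening of 5.8 keeps one with a prespecified event, and 7.1 keeps one with any component event. Two programmers could produce different denominators from the same data.

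**Working it through.** **Inputs from the documents.** N = 109 treated and 98 evaluable at 6 months (SAP 3.1.3); attrition of at most 10% at 6 months for all reasons (Protocol 10.3); visit window of 14 days (Protocol 11.1); post-embolization syndrome 24.7% (Protocol Table 19.1-1), used only to choose a realistic event count.

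**Assumptions.** 27 subjects have the event before day 16 and none later. Attrition at 12 months is not given, so a range is shown.

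**The plan's own figures.** The SAP states no adverse-event rate to reproduce. The attrition does reproduce: 98/0.90 = 108.9, so 109, which means 109 − 98 = 11 exits by 6 months. The lower windows also match: 30 − 14 = 16, 91 − 14 = 77, 183 − 14 = 169, 365 − 14 = 351.

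**Formula.** Let E be the subjects with the event by the cut-off, and L the event-free subjects who leave before the lower window. The SAP rate is E/(N − L). When every event precedes every exit, Kaplan-Meier and cumulative incidence both equal E/N = 27/109 = 24.8% at every cut-off. The relative inflation is N/(N − L).

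**Results if every exit is event-free (upper bound).**

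| Row | Exits L | Source of L | SAP rate | Inflation |
|---|---|---|---|---|
| 6 months | 11 | documented 10% | 27/98 = 27.6% | 109/98 = 1.11 |
| 12 months | 16 | assumed 15% | 27/93 = 29.0% | 109/93 = 1.17 |
| 12 months | 22 | assumed 20% | 27/87 = 31.0% | 109/87 = 1.25 |
| 12 months | 33 | assumed 30% | 27/76 = 35.5% | 109/76 = 1.43 |

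**If exits are spread evenly over subjects with and without the event.** Only the 82 event-free subjects can be lost. At 10%, 20% and 30%, 74, 66 and 57 of them remain. The rates are 27/101 = 26.7%, 27/93 = 29.0% and 27/84 = 32.1%.

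**Effect of the conflicting wordings.** Suppose that 3 of the 11 exits by 6 months and 8 of 22 by 12 months are deaths (assumed). Under 5.8.2, subjects who died without the event are dropped: 27/98 = 27.6% and 27/87 = 31.0%. If 7.1 keeps them, the denominators lose only the 8 and 14 withdrawals: 27/101 = 26.7% and 27/95 = 28.4%. Both sets exceed 24.8%, so withdrawals inflate the rate under either wording.

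**The 30-day row.** Adequate follow-up is 16 days, so a subject who leaves on days 16 to 29 counts as event-free to day 30 with up to 30 − 16 = 14 days unobserved. This works in the opposite direction and affects few subjects.

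**The case against.** The strongest reply concerns scope. SAP 5.8 ties the rule to rates specified in a Safety Plan that is not among these documents. The three events it names are observed over 6 weeks, when little attrition is expected. The secondary endpoint is described only as a frequency, in the same words in protocol and SAP. A reader might infer that the SAP has replaced the protocol's frequency with the adequate-follow-up rate; the documents do not say so. What stands is narrower. SAP 5.9 plans exact-day rates for all site-reported events without a denominator, and 5.8.2 and 7.1 are the only rules available to a programmer.

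A reader might also infer that subjects who die are always dropped. That cannot be so for the all-cause death rate. Under the opening of 5.8 or under 7.1, a subject who died may stay in for other events too. The loss of withdrawals holds under every wording.

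The cumulative reading can be questioned: counting late events at the next visit, and the reference in 7.1 to an analysis interval, could mean separate intervals. An early event would then be absent from later rows. The column of maximum days to event in 5.8.2 and the procedure-date origin favour the cumulative reading, but the text does not settle it.

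On size, the documented 6-month effect is under 3 percentage points. The standard error of 27/109 is √(0.248 × 0.752/109) = 4.1 points. The later-row bias overstates toxicity, so it is conservative for the device. These points limit the importance of the concern; they do not remove a systematic bias that a standard estimator avoids.

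**Conclusion.** The concern holds for cumulative binary safety rates at the later time points. At documented attrition the 6-month inflation is at most about 1.11-fold, for example 24.8% to 27.6%. At 12 months it could reach 1.17- to 1.43-fold, but only under an assumed attrition of 15% to 30% with all exits event-free. The direction is upward at later rows and slightly downward at 30 days.

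The conclusion rests on two readings: that numerators accumulate from the procedure, and that 5.8.2 and 7.1 govern the rates in 5.9. Both are the more natural reading, but neither is stated outright.

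It would go too far to say that the rule defeats a planned comparison with Protocol Table 19.1-1. That table gives no time horizon or denominator, and no such comparison is planned. The primary response analysis, the sample size and the success criterion are unaffected, and the 6-week safety triggers are little affected. This should be corrected, but it does not threaten the trial's main conclusion.

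**What to change.** In SAP 5.8, 5.9 and 7.1:

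- Report the overall adverse-event frequency with all subjects who received the first Tandem treatment as denominator, in line with the analysis sample in SAP 4.1.
- For rates at 30, 91, 183 and 365 days, replace the adequate-follow-up rate, or make it secondary. Use Kaplan-Meier for all-cause death, and cumulative incidence with death as a competing event for the others. Censor withdrawals at last contact. The all-treated denominator should not be used for these dated rates, because it would count early withdrawals as event-free.
- Reconcile the denominator wordings in 5.8, 5.8.1, 5.8.2 and 7.1, and state that events are cumulative from the procedure if that is intended.

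SAP 7.1 already derives the last follow-up date and days to event, and SAP 5.7.1 already plans Kaplan-Meier for death. The cost is SAP wording and a little extra programming, with no new data.

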5.8.3 Missing Event Dates Considerations

All event rates will be calculated relative to the date of procedure (i.e. post-procedure).

When calculating rates of adverse events with missing event date (i.e. mm/dd/yyyy), the ideal is to work with safety and/or data management representatives to query sites for missing data. However missing and partial missing dates may be handled as using the worst case scenario as follows:

Partial Date Description	Action Taken
Entire onset date is missing	The procedure date will be used for the onset date.
The month and the day of the month are missing but the year is available	January 1 st will be used for the month and day of the onset date. However, if the imputed date falls before the procedure date, then the procedure date will be used for the onset date.
Day is missing, but the month and year are available	The 1 st will be used as the day of the onset date. However, if the imputed date falls before the procedure date, then the procedure date will be used for the onset date.

